3.3 Subject Eligibility (Inclusion and Exclusion Criteria)

Subjects who have an existing *non-study* contralateral total hip replacement greater than 3 months postoperatively at the time of consent may be entered into this study if they qualify based upon the criteria for inclusion and the approved labeling requirements for the Pinnacle/Corail or Pinnacle/Actis devices. Simultaneous or staged bilateral patients are not allowed in this study (see **Exclusion Criteria #9**). Only one hip can be enrolled per subject.

Inclusion Criteria

Confidential Version Date: 040CT2021 The decision to have hip replacement with the study devices is part of the patient's standard of care path regardless of the research. Subjects meeting all of the following criteria will be considered for participation in the study:

- The patient is undergoing a standard of care primary cementless hip replacement with the Pinnacle cup and a Corail or Actis stem via the Anterior Advantage approach. All devices are to be used according to the approved indications.
- 2) Individuals who are able to speak, read, and comprehend the Institutional Review Board approved Informed Consent Document and willing and able to provide informed patient consent for participation in the study and have authorized the transfer of his/her information to DePuy Synthes.
- 3) Individuals who are willing and able to complete follow-up visits and questionnaires as specified by the study protocol.
- 4) Individuals who are not bedridden per the discretion of the investigator (The intent of "not bedridden" means a permanent situation, not a temporary situation as in a hip fracture or trauma case).
- 5) Individuals who are a minimum age of 21 years at the time of consent.

Exclusion Criteria

Subjects will be excluded if, in the opinion of the Investigator, the individual meets any of the following exclusions:

- 1) Active local or systemic infection.
- 2) Loss of musculature, neuromuscular compromise or vascular deficiency in the affected limb rendering the procedure unjustified.
- 3) Poor bone quality, such as osteoporosis, where, in the surgeon's opinion, there could be considerable migration of the prosthesis or a significant chance of fracture of the femoral shaft and/or the lack of adequate bone to support the implant(s).
- 4) Charcot's or Paget's disease.
- 5) The Subject is a woman who is pregnant or lactating.
- 6) Subject had a contralateral amputation.

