3.4 Enrollment, Randomization & Subject Identification (ID) Number

A patient will be enrolled in the study after signing the Institutional Review Board (IRB) approved informed consent form.

Each enrolled patient will be assigned a unique Subject identification number by the database. The first two digits of the Subject number represent the site identification number, followed by a hyphen, and three digits representing the sequential identification (*e.g.*, Subject 10-001 is the first number assigned at site 10). The Subject's unique identifier assigned in EDC will be recorded on each page of the eCRF and other study-specific documentation relating to that Subject (e.g. CRF source documents, patient reported outcomes, etc.). Subject numbers will be assigned for all patients who consent to participate in the study.

After the subject is consented, it must be verified that the subject meets all eligibility criteria. Once confirmed, the subject will be randomized into a treatment group. The sponsor will provide stickers in numerical order for each site. The stickers should be removed in numerical order to reveal the randomization code and treatment group for each consecutive consented subject that meets eligibility criteria. The sticker should be placed on the screening log to document that randomization was unbiased. The planned randomization group should then be documented in the applicable source document and on the Randomization eCRF (eCRF RDM) in the database. The subject will be randomized to either the Control – Anterior Advantage *without* KINCISE or the STUDY – Anterior Advantage *with* KINCISE group.

The flowchart presented below in Figure 3-1 depicts the process flow for screening, enrollment and randomization for the study.

The Principal Investigator must document the Subject's participation in this study in the Subject's clinic and hospital notes. If the subject is randomized to KINCISE, the surgeon should use KINCISE for the femoral broaching and as much as possible throughout the study where a mallet would have typically been used. However, if the surgeon feels it is necessary to use a mallet (i.e. impaction of the cup). Each use of the mallet should be documented on the Operative Details eCRF and in the source documents. If the surgeon uses the mallet as described above, it would not be considered a protocol deviation as long as KINCISE was used for the femoral broaching and as much as possible (per the randomization

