Sticker sheets were created, one set for up to 30 sites, containing treatment assignments for 120 subjects using a fixed block size of 4 and a treatment allocation ratio of 1:1. On the face of each sticker is a character in the sequence A, B, C,, X, Y, Z, AA, AB, AC,AX, AY, AZ, BA, BB, BC, etc...., BX, BY, BZ, CA, etc...

The stickers should be removed sequentially to reveal the randomization code and treatment group ('Study (Kincise)' or 'Control (Mallet)') for each consecutive consented subject that meets eligibility criteria. Peeled sticker should be placed on the screening log to document that randomization was unbiased. The planned randomization group should then be documented in the applicable source document and on the Randomization eCRF (eCRF RDM) in the database.

The assigned treatment will remain secret to site personnel until subject is found to meet all eligibility criteria; No other blinding is implemented in this study.

4 Interval Windows

The study includes the following periods: Pre-op, Operative, Immediate post-op, 6 Week, 24 Week. Intervals related to each are shown in Table 3, below.

Visit	Minimum Day	Maximum Day	Midpoint Day
Pre-Op	-180	0	
Operative	0	0	0
Immediate post-op	0	Discharge	
6 week	14	60	37
24 week	61	200	130

 Table 3
 Interval Windows for Non-Radiographic Study Visits

Time point specific data collected to satisfy the primary and secondary efficacy-related objectives will be assessed for compliance with these intervals. Only data which can be attributed to the visit intervals in Table 3 will be used in the analysis of primary and secondary endpoints. This visit will be hereafter referred to as the Analysis Visit and the originally recorded visit as the Nominal Visit. If multiple measurements fall into the pre-operative window, or into the 'Immediate post-op' post-operative window, the result collected most proximate to surgery will be utilized. For the '6 week' and '24 week' visits, if multiple measurements fall into the window will be utilized for analysis.

5 Levels of Significance

The level of significance is 95%. Primary endpoint analyses, further described in section 8.7, and secondary endpoint analyses with hypotheses, further described in 8.8, will use 1-sided 95% confidence intervals and associated p-values. Data summaries of secondary endpoints without hypotheses and of exploratory endpoints will use 2-sided 95% confidence intervals and associated p-values.

6 Analysis Sets

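### Fixed blocks of 4 at each open-label site leave up to one third of allocations certain in advance, if site staff know or work out the block size

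*SAP*

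**What the plan says.** SAP section 3 (Randomization and Blinding Procedures) describes the lists: "Sticker sheets were created, one set for up to 30 sites, containing treatment assignments for 120 subjects". Allocation is 1:1, and the lists were generated "using a fixed block size of 4". Protocol 3.4 confirms that supply is by site: "The sponsor will provide stickers in numerical order for each site". Both documents require strict sequential use; in the Protocol's words, "The stickers should be removed in numerical order to reveal the randomization code and treatment group". The peeled sticker goes on the screening log, and Protocol 3.2 keeps the original of that log at the site.

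The SAP withholds the assignment from site staff until eligibility is confirmed, and then adds: "No other blinding is implemented in this study". Neither document describes varying block sizes or central allocation. The block size appears in the SAP but not in the Protocol text supplied.

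Protocol 3.3 makes all exclusions a matter of the investigator's opinion. One of them, on bone quality, applies where "in the surgeon's opinion, there could be considerable migration of the prosthesis" or where femoral shaft fracture is a significant risk.

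**The concern.** Each site holds its own complete, ordered allocation history and knows every past assignment. In blocks of 4 the arms balance after every fourth sticker, so a site that looks can find the pattern without being told the block size. From then on the last place in each block is certain, and sometimes the third as well. Confirming eligibility before peeling does not protect against this, because the next arm can be known before the sticker is lifted.

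At stake is who enters each arm. If the next arm is predictable while eligibility still involves judgement, easier or harder femurs could go preferentially to one arm. Broaching time, the primary endpoint, would then be compared between unlike groups. The planned analysis would not reveal it: the primary test is an unadjusted two-sample t-test on the Per Protocol set (SAP 8.7), with no sensitivity analyses (SAP 8.13) and no assessment of site homogeneity (SAP 8.15).

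**Working it through.** The plan states no predictability figure, so there is none to reproduce.

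**Inputs**
- Fixed block of 4 at 1:1, giving 6 equally likely orders (SAP section 3).
- A separate list at each site (Protocol 3.4). The SAP wording is read the same way, since one shared list of 120 could not supply 400 subjects.
- About 40 subjects per site, or 10 blocks (Protocol 5.1).
- SD 2.5 minutes, 200 per arm, margin 1.25 minutes (SAP section 7).

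**Certain allocations.** An allocation is certain once one arm's two places in the block are used. In 2 of the 6 orders (AABB, BBAA), positions 3 and 4 are certain; in the other 4 orders only position 4 is.

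(2 × 2 + 4 × 1)/6 = 4/3 per block; (4/3)/4 = 33.3%.

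**Best-guess rate.** Always guess the arm with more places left and toss a coin on ties. The chance of being right at positions 1 to 4 is 1/2, 2/3, 2/3 and 1.

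(1/2 + 2/3 + 2/3 + 1)/4 = (17/6)/4 = 70.8%, against 50% with no information.

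**Per site of 40.** Certain: 10 × 4/3 = 13.3. Correct guesses: 10 × 17/6 = 28.3, against 20 by chance. These are ceilings, because they apply from the first subject. If, as an assumption, three blocks pass before the pattern is noticed, 28 subjects remain and 28/3 = 9.3 allocations are certain.

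**What it could mean in minutes (illustrative).** Suppose staff shift the expected broaching time by η minutes in the favoured direction according to the predicted arm. The documents give no value for η.
- Acting on every guess: bias in the mean difference = 2η(2 × 0.708 − 1) = 0.83η.
- Acting only on certain allocations: 2η × 1/3 = 0.67η.
- SE = 2.5 × √(2/200) = 0.25 minutes, so one-sided superiority at 5% needs a difference of about 1.645 × 0.25 = 0.41 minutes.
- With η = 0.5 on every guess, bias = 0.42 minutes, one third of the margin. With no true difference, the chance of claiming superiority would be about 50% instead of 5%.
- For η from 0.25 to 1.0, bias runs from 0.21 to 0.83 minutes. Using up the whole 1.25-minute margin needs η = 1.25/0.83 = 1.5 minutes on every guess.

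**Alternatives.** Fixed blocks are enumerated exactly. Mixed blocks are simulated for lists of 40, with a best guesser who knows the set of sizes but not their order.

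| Scheme | Certain | Best guess correct |
|---|---|---|
| Fixed 4 (plan) | 33.3% | 70.8% |
| Fixed 6 | 25.0% | 68.3% |
| Fixed 8 | 20.0% | 66.6% |
| Mixed 4, 6 | about 5.6% | 68.9% |
| Mixed 4, 6, 8 | about 2.3% | 67.6% |

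For steering on every guess, mixing 4, 6 and 8 lowers the bias only from 0.83η to 2η(2 × 0.676 − 1) = 0.70η. For steering on certain allocations alone it falls from 0.67η to 2η × 0.023, about 0.05η.

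**The case against.** The strongest reply is that prediction needs knowledge the sites may not have. The Protocol text supplied does not give the block size, and nothing shows that sites receive the SAP. A reader might infer that one third of the trial, about 133 of 400 subjects, will be allocated with the arm already known, or that selection has occurred. The documents support neither. The count would require every site to know the block size from its first subject and to track its place in each block, and no passage points to actual steering. What stands is that the pattern can be found from a log the site itself keeps.

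The plan also has relevant controls. Protocol 3.2 requires consent before screening and a log of the screening date, the result and the main reason for non-inclusion, copied regularly to the sponsor. Stickers go to consecutive eligible subjects. Steering by exclusion would therefore leave a trail. This deters and helps detect, but does not prevent prediction.

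The bone-quality exclusion is a narrow criterion, not a free choice between easy and hard femurs. That is fair, although the investigator's opinion governs the whole exclusion list.

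Non-inferiority is hard to overturn this way. η = 1.5 means a 3-minute gap between cases steered to each arm, or 1.2 of the planned SDs, on every guess. That stands, and it makes the superiority test the more exposed claim.

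Finally, tight balance within sites has value when the analysis is unadjusted and stem choice follows the surgeon or site. That is a legitimate trade-off, but the loss from mixed blocks is small.

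**Conclusion.** The concern holds as a conditional risk to concealment. If site staff know or infer the block size and track the log, up to 33.3% of allocations are certain in advance and up to 70.8% can be guessed, which is at most about 13 certain per 40-subject site. Both percentages are exact for a fixed 1:1 block of 4, but they are averages over blocks and ceilings on what a site could know. They rest on separate site lists, open allocation history and a best guessing strategy. Any effect in minutes depends on an assumed amount of steering for which the documents give no evidence.

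This is a cheap improvement worth making where stickers remain, not grounds for saying that the primary comparison is biased. Most of the benefit is the near removal of certain allocations; overall guessability changes little.

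**What to change.** For sites not yet activated, and for unused whole blocks elsewhere, reissue stickers with randomly varying block sizes, for example 4, 6 and 8. Describe the scheme in general terms and keep the sizes out of any document the sites see. The SAP says the sheets already exist, so the change can reach only unused stickers; the documents do not show how many remain.

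The cost is regenerating and reprinting sheets, and a maximum within-site imbalance of 4 instead of 2. No extra subjects are needed.

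If all stickers are used, state the limitation in the report and compare femoral bone class and DORR class between arms as a check for selection. SAP 8.4 already lists both among the operative details, so this needs no new data. They are recorded in an open-label trial, so the comparison supports a judgement but does not settle it.

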5.2 Study Database

The study database has been validated in accordance with 21 CFR Part 11. Prior to being released for importation of study data, validation of the study level components will be conducted in accordance with approved user acceptance testing procedures. Access to this system will be controlled so that only authorized users will have the ability to enter into the system. The system is considered a closed system according to 21 CFR Part 11 Electronic Records; Electronic Signatures.

6 Radiographs

The radiographs collected for this study will be sent to Medical Metrics, Inc. (MMI) for third party review. This study will accept radiographs for the preoperative interval taken prior to the study Subject's participation in this study up to 180 days before surgery as long as the radiographs meet the three

Confidential Version Date: 040CT2021 DePuy Synthes Protocol DSJ_2019_03 / Version 2.0 / TV-eFRM-02920 Page **22** of **53** protocol required views: Antero-Posterior (AP) Long Leg or AP Pelvis (bilateral), AP Hip (unilateral), and Lateral. Preoperatively, weight-bearing AP Pelvis and AP Hip and Modified Lauenstein views are preferred, but not required. The 180 day preoperative window is allowed in order to minimize a study subject's unnecessary exposure to radiation, therefore, standard of care views will be accepted preoperatively if imaging has already been acquired before the subject was consented for the study. For all post-operative intervals, weight-bearing AP Hip and AP Pelvis, and Lateral films are required. The Modified Lauenstein view is preferred postoperatively but a Lauenstein lateral or cross-table lateral view will be accepted in instances where the view cannot be collected due to subject positioning constraints. Further radiographic details will be available in the radiographic protocol separate to this document.

7 Subject Evaluations

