8.8 Secondary Endpoints and Associated Hypotheses

All secondary endpoint analyses and associated hypotheses will be conducted on the Per Protocol Analysis Set.

If the primary endpoint analysis successfully demonstrates non-inferiority of femoral broaching time, regardless of whether the above test of superiority was successful or not, then the following three secondary endpoint analyses will be conducted under a gatekeeping strategy, in this specified order, where testing is performed in sequence and continues until a null hypothesis is not rejected or all hypotheses have been tested, each with a 1-sided alpha of 0.05:

- 8.8.1 Skin-to-skin OR time
 - Skin-to-skin OR time in minutes will be summarized as a continuous variable for both treatments and combined
 - A non-inferiority test of skin-to-skin OR time will be conducted with a noninferiority margin of 3.75 minutes, using a 2-sample t-test:
 - Null Hypothesis: $H_0: \mu_I \ge \mu_C + 3.75$
 - Alternative Hypothesis: H_A : $\mu_I < \mu_C + 3.75$
 - where μ_I and μ_c are mean skin-to-skin OR times with and without KINCISE, respectively. The null hypothesis will be rejected and non-inferiority will be concluded if the 1-sided upper 95% confidence limit for the μ_I μ_c difference (based upon a 2-sample t-test) is less than 3.75
 - The 1-sided upper 95% confidence limit for the difference and the pvalue will be presented.
- 8.8.2 The percent of subjets with acetabular cup abduction angle within +/- 10 degrees of plan
 - The proportion of subjets with acetabular cup abduction angle within +/- 10 degrees of plan will be summarized for both treatments and combined
 - A non-inferiority test of the percent of subjects with acetabular cup abduction angle within +/- 10 degrees of plan under a NI margin of 10% will be conducted:
 - Null Hypothesis: $H_0: P_I \le P_C 10\%$
 - Alternative Hypothesis: $H_A: P_I > P_C 10\%$
 - where P_I and P_c are the percentages of subjects with acetabular cup abduction angle within 10% of plan with and without KINCISE, respectively. The null hypothesis will be rejected and non-inferiority will be concluded if the 1-sided lower 95% confidence limit for the P_I –

 P_{C} difference (based upon a normal approximation method) is greater than -10%

- The 1-sided lower 95% confidence limit for the difference and the pvalue will be presented.
- 8.8.3 The percent of subjects with acetabular cup version angle within +/- 10 degrees of plan

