8.8.9 Hip Evaluation Functional Recovery Outcomes

All questions on the hip evaluation functional recovery outcomes will be summarized as categorical data using the Per Protocol Analysis Set in the following fashion: recovery time will be the first week (Week 1 – After Week 12) recovery was achieved; Otherwise, recovery time will be "Still cannot do" or "Not Applicable/I never do this" if subject selected these options at the last visit subject was seen.

8.8.10 Radiographic Outcomes (based upon: AP Hip, AP Pelvis, and Lateral) at week 6, week 24

The following radiographic endpoints will be summarized at week 6 and at week 24: Acetabular cup version – Hip, Acetabular cup version – Pervis, Acetabular cup Inclination, Acetabular cup migration, Acetabular cup radiolucency, Acetabular cup osteolysis, Acetabular cup scerotic lines, Acetabular cup porous coating integrity, Femoral stem position, Femoral stem tilt, Femoral stem subsidence, Femoral stem radiolucency, Femoral stem osteolysis, Femoral stem osteolytic lines, Femoral stem coating integrity, Calcar resorption, Calcar fracture, Heterotopic ossification, Proximal femur, Pelvis vertical alignment, Device/anatomy condition.

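### SAP 3 as written excludes masking of the third-party radiograph readers, on whose films two confirmatory cup-angle tests rest; masking them needs no extra reader or read

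*SAP*

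**What the plan says.** SAP 3 (Randomization and Blinding Procedures) makes one concealment provision: "The assigned treatment will remain secret to site personnel until subject is found to meet all eligibility criteria". It then closes the subject: "No other blinding is implemented in this study".

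Protocol 6 (Radiographs) says that study films "will be sent to Medical Metrics, Inc. (MMI) for third party review". It gives views and time windows but nothing on what the reader may know. It adds: "Further radiographic details will be available in the radiographic protocol separate to this document".

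SAP 8.8.10 treats cup position as a radiographic outcome: "The following radiographic endpoints will be summarized at week 6 and at week 24: Acetabular cup version", with cup inclination also on the list. In SAP 8.8, once the primary test succeeds, "then the following three secondary endpoint analyses will be conducted under a gatekeeping strategy". The second and third of these (8.8.2 and 8.8.3) concern the percentage of subjects within 10 degrees of plan for abduction and for version, each with a 10-point margin.

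Protocol 7.1 records planned inclination and anteversion before surgery. It also lets sites that template as standard of care submit their templates together with the pre-operative films.

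**The concern.** The surgeon holds the tool and cannot be blinded, so broaching time and skin-to-skin time are necessarily open-label. The cup angles differ: they are taken from films that leave the site, and both arms receive a Pinnacle cup with a Corail or Actis stem (Protocol 1 and 5.1), so the implant systems do not reveal the arm. They are the confirmatory endpoints that can readily be assessed without knowledge of treatment, yet the blinding section rules out any blinding beyond pre-eligibility concealment.

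Each angle is a measurement converted to success or failure at a fixed 10-degree limit, so small differences in reading can reclassify borderline hips. Shifts that differ between arms could produce a false non-inferiority claim or cost the sponsor a true one. SAP 8.13 plans no sensitivity analysis that might reveal either.

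**Working it through.** **1. Side-by-side reading.**

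| Question | What the documents give |
|---|---|
| Is any assessor masked? | SAP 3: nothing beyond concealment before eligibility |
| Who reads the films? | Protocol 6: an outside third party; masking not mentioned |
| Are the cup angles read from films? | SAP 8.8.10 lists cup version and inclination as radiographic; that the vendor supplies the two confirmatory angles is inferred from this and Protocol 6 together |
| Is the reader told the arm? | Not stated anywhere |
| Can the planned position reach the vendor? | Possibly, through optional templates (Protocol 7.1) |
| Could masking be specified elsewhere? | Yes, in the radiographic protocol, which is not available |

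**2. The plan's own power figure.** Inputs from SAP 7: 200 per group, margin 10 points, one-sided alpha 0.05, anticipated rates of 90% to 95% (abduction) and 91% to 92% (version). The method is the normal approximation with equal true rates p:

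power = Φ(0.10 / √(2p(1−p)/200) − 1.645)

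- p = 0.90: SE = √(2 × 0.90 × 0.10/200) = 0.0300; Φ(3.333 − 1.645) = Φ(1.688) = 95.4%
- p = 0.91: 96.8%
- p = 0.92: 97.9%
- p = 0.95: 99.8%

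The stated figure of about 95% reproduces at the low end. Masking changes none of N, alpha or power.

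**3. Illustration: shift towards KINCISE at the margin.** The documents give no reader-bias figure, so the net shift b is assumed. With control at 90% and KINCISE truly at 80%, the observed KINCISE rate is 0.80 + b:

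type I error = Φ(b/SE − 1.645), SE = √(0.90 × 0.10/200 + (0.80+b)(0.20−b)/200)

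| b | SE | b/SE | One-sided type I error |
|---|---|---|---|
| 0 | 0.0354 | 0 | 5.0% |
| 1 point | 0.0349 | 0.286 | 8.7% |
| 2 points | 0.0345 | 0.580 | 14.3% |
| 3 points | 0.0340 | 0.883 | 22.3% |

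**4. Illustration: shift against KINCISE.** With both true rates at 90%, power = Φ((0.10 − b)/SE − 1.645), where SE now uses a KINCISE rate of 0.90 − b. Shifts of 1, 2 and 3 points reduce power from 95.4% to 90.2%, 81.9% and 70.9%.

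**5. How degrees translate into points.** Assume normal errors about plan. The SD is 6.1 degrees if 90% fall within 10 degrees and 5.1 degrees if 95% do.

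| Assumed reading error in one arm | 1 degree | 2 degrees |
|---|---|---|
| Every near-miss moved towards its own target (limit in effect 11 or 12 degrees) | +1.9 to +3.0 points | +3.1 to +5.2 points |
| All readings shifted the same way | about −0.4 to −0.5 points | about −1.8 to −1.9 points |

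The sign depends on the form of bias assumed. The first row needs a reader who knows both the arm and the target and moves every borderline hip favourably. That is a worst case, not an expected value.

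**The case against.** A reader might infer that the vendor's readers are in fact unmasked, or that the sponsor decided to unmask them. The documents do not support that. The closing clause of SAP 3 follows a statement about site personnel, in a section on stickers and allocation. Reader procedures would naturally sit in the radiographic protocol. No route from arm to reader is shown either: the assignment is held on the screening log, in source documents and on the randomization eCRF; treatment received is on the operative eCRF; subject numbers carry only site and sequence (Protocol 3.4). Nothing says that operative notes travel with the films.

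Further limits also stand. How the angles are measured is not described. The templates are optional and can come from either arm, so knowing the target without the arm would not by itself favour one arm. Protocol 10.9.4 summarises the difference from plan per subject and does not have the reader judge success. The reader is already independent of the sites. The endpoints are secondary, and trial success rests on broaching time.

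What does not stand is the idea that the SAP is merely silent. Its sentence covers the whole study and contains no exception for readers. If the radiographic protocol masks them, the two documents conflict and SAP 3 still needs correcting. If it does not, an available protection is missing. In neither case could a report cite this plan as support for masked assessment.

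**Conclusion.** The point holds as a defect in the plan's provisions, not as a finding that bias exists. As written, SAP 3 excludes masked reading, and neither it nor Protocol 6 protects the measurements behind two of the three confirmatory secondary tests. This rests on taking the SAP sentence at face value and on the inference that the third party supplies the cup angles.

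The size of any bias is unknown. The rise in type I error to about 9% to 22% is conditional on an assumed net 1 to 3 point shift at a 90% control rate, with KINCISE exactly at the margin; it is not an estimate. The primary endpoint is unaffected. The change is worth making because the exposure concerns confirmatory claims and the remedy is small.

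Masking would not secure the whole endpoint. SAP 8.4 records that inclination and version targets can be changed during surgery, by a surgeon who knows the arm. That leaves the planned value open to influence and is a separate weakness.

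**What to change.** Keep the statement on concealment before eligibility and the disclosure that surgeons and sites are unblinded. Amend only the last clause of SAP 3, to read:

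> No other blinding is implemented, except that third-party radiograph readers are masked to treatment group and to the planned cup angles; films are sent under subject ID only, any pre-operative templates are withheld from the cup-angle reader, and deviation from plan is computed in the database.

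State the same in Protocol 6, and check and align the radiographic protocol. If that document already masks the readers, the change simply removes the conflict.

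The cost is wording in the SAP and protocol and a transmittal instruction to sites and the vendor. The documents give no cost figure, but no extra reader, read or subject is needed.
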